- Chronic use of antibiotics for prevention of AECOPD (*e.g.* azithromycin).
- Receiving oxygen therapy.
- Planned lung transplantation.
- Planned/ underwent lung resection surgery (*e.g.* lung volume reduction surgery or lobectomy).
- Diagnosis of α -1 antitrypsin deficiency as the underlying cause of COPD.
- Diagnosed with a respiratory disorder other than COPD (such as sarcoidosis, active tuberculosis, clinically significant bronchiectasis, lung fibrosis, pulmonary embolism, pneumothorax, current diagnosis of asthma in the opinion of the investigator), or chest X-ray/ CT scan revealing evidence of clinically significant abnormalities not believed to be due to the presence of COPD. Subjects with allergic

rhinitis do not need to be excluded and may be enrolled at the discretion of the investigator.

- History of any reaction or hypersensitivity likely to be exacerbated by any component of the vaccines and/ or the bronchodilator used for spirometry assessment during the study.
- Contraindication for spirometry testing (such as recent eye surgery, recent thoracic or abdominal surgery procedures, unstable cardiovascular status, recent myocardial infection or pulmonary embolism).
- Clinically significant* abnormality in haematology (haemoglobin, platelets or WBC) or biochemistry parameter (ALT, AST or creatinine), as per the judgement of the investigator.

* As the study participants are COPD patients, various pre-existing haematological/biochemical abnormalities might be detected. The investigator should use his/ her clinical judgement to decide which ones are clinically significant.

- Acute cardiac insufficiency.
- Malignancies within the previous 5 years (excluding non-melanotic skin cancer and carcinoma *in situ* of the cervix, if considered cured) or lymphoproliferative disorder.
- Any known disease or condition likely to cause death during the study period.
- Acute disease and/ or fever at the time of Screening.
 - Fever is defined as oral or axillary temperature $\geq 37.5^{\circ}\text{C}$. The preferred route for recording temperature in this study will be oral.
 - Subjects with acute disease and/ or fever at the time of Screening may be enrolled at a later date if enrolment is still open. Subjects with a minor illness without fever may be enrolled at the discretion of the investigator.
- Pregnant or lactating female.
- Current alcoholism and/ or drug abuse.

Refer to the [glossary of terms](#) for the definition of alcoholism.

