6.2.2.2. Treatment allocation to the subject

The treatment numbers will be allocated by dose.

6.2.2.2.1. *Study group and treatment number allocation*

The target will be to enrol approximately 140 eligible subjects who will be randomly assigned to the 2 study groups in a (1:1) ratio (approximately 70 subjects in each group).

Allocation of a subject to a study group at the investigator site will be performed using a centralised randomisation system on the internet (SBIR). The randomisation algorithm will use a minimisation procedure accounting for age (40 - 59 years or 60 - 80 years), number of moderate/ severe AECOPD in the previous year (< 2 or \geq 2) and GOLD grade (GOLD 2 or GOLD 3). All factors will have equal weight in the minimisation algorithm.

At Visit 1, before administration of vaccine Dose 1 to eligible subjects who signed and dated the ICF at the Screening Visit, the dedicated site staff will access SBIR. Upon providing the subject's age category (40 - 59 years or 60 - 80 years), number of moderate/ severe AECOPD in the previous year and his/ her GOLD grade, the randomisation system will determine the study group and will provide the treatment number to be used for the first dose.

The number of each administered treatment must be recorded in the eCRF on the Vaccine Administration screen.

When SBIR is not available, refer to the SBIR user guide or the SPM for specific instructions.

6.2.2.2.2. *Treatment number allocation for subsequent doses*

For each dose subsequent to the first dose, the dedicated study staff will access SBIR. Upon providing the subject identification number, the system will provide a treatment number consistent with the allocated study group.

The number of each administered treatment must be recorded in the eCRF on the Vaccine Administration screen.

When SBIR is not available, refer to the SBIR user guide or the SPM for specific instructions.

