At each AECOPD visit: a volume of approximately 2 mL of whole blood will be collected for haematology parameters from all subjects ([Table 10](#)). They should be kept at room temperature and shipped on the day of collection.

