6.7.3. Laboratory assays

Refer to [APPENDIX A](#) for a detailed description of the assays performed in the study.
Refer to [APPENDIX B](#) for the address of the clinical laboratories used for sample analysis.

Haematology/ biochemistry

Haematology/ biochemistry assays for safety assessment will be performed in a central laboratory. Haematology assays on whole blood taken at AECOPD visits will be performed in the same central laboratory.

Table 11 Haematology and biochemistry

System	Discipline	Component	Method	Scale	Laboratory*
Whole blood	Haematology	Haemoglobin	commercial	Quantitative	Central laboratory
		Platelets	commercial	Quantitative	
		White Blood Cells (WBC) **	commercial	Quantitative	
Serum	Biochemistry	Alanine Aminotransferase (ALT)	commercial	Quantitative	Central laboratory
		Aspartate Aminotransferase (AST)	commercial	Quantitative	
		Creatinine	commercial	Quantitative	

*Refer to [APPENDIX B](#) for the laboratory address.

** Including WBC differential count.

Humoral antibody responses (Amended 15 April 2016)

Total IgG concentrations will be measured by ELISA at GSK Biologicals' laboratory. Standardised procedures will be used for all assays.

Table 12 Humoral Immunity (Antibody determination) (Amended 15 April 2016)

System	Component	Method	Kit / Manufacturer	Unit	Cut-off	Laboratory*
Serum	Anti-PD	ELISA	In house	EL.U/mL	153	GSK Biologicals**
Serum	Anti-PE	ELISA	In house	EL.U/mL	8	GSK Biologicals**
Serum	Anti-PilA	ELISA	In house	EL.U/mL	7	GSK Biologicals**

EL.U/mL = ELISA unit per millilitre

*Refer to [APPENDIX B](#) for the laboratory addresses.

** GSK Biologicals laboratory refers to the **Clinical Laboratory Sciences (CLS)** in Rixensart, Belgium; Wavre, Belgium.

Serum and plasma samples might also be used for **development and/ or evaluation of other assays** to measure the immune response to the investigational NTHi vaccine components and/or to other NTHi antigens such as, but not limited to, bactericidal activity assay, assays measuring functional antibodies, immunochemistry assays for other immunoglobulin classes and/or for anti-IgG subclasses.

Additional testing on serum and plasma samples may be done during the study or after study completion, should these data be required for accurate interpretation of the data and/ or for further research related to the investigational vaccine and/ or the disease, should such test(s) become available at GSK Biologicals' laboratory or a laboratory designated by GSK Biologicals.

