Appendix A Laboratory assays

Humoral antibody responses

Anti-PD antibodies

Anti-PD antibodies will be determined using an ELISA assay developed by GSK Biologicals. Concentration of specific anti-PD antibodies will be determined, using in-house made reference serum. The **current** cut-off of the assay is 100 EL.U/mL. ***This assay will however be re-validated according to the latest validation standards and a new cut-off might be defined based on a precise and accurate limit of quantification.***

GlaxoSmithKline Biologicals	
Clinical Research & Development Protocol Amendment 2	
eTrack study number and Abbreviated Title	200157 (NTHI-004)
EudraCT number	2013-003062-13
Amendment number:	Amendment 2
Amendment date:	15 December 2014
Co-ordinating author:	PPD (XPE Pharma & Science for GSK Biologicals)
Rationale/background for changes:	
Protocol amendment 2 was prepared:	

 • To add clarification in the tertiary objectives: because acute exacerbations of COPD are complex events, triggered by multiple (interacting) pathogens, assessing the natural immunity to other pathogens might be important for interpretation of the data. • To add an additional blood sample for haematology assessment at each AECOPD visit. This blood sample will be collected to describe the systemic inflammation at time of exacerbation in terms of white blood cells and differential cell counts. • To clarify the list of concomitant medication that may lead to elimination of a subject from ATP analysis of immunogenicity (Section 7.6.2): because oral corticosteroids are commonly used in treatment of exacerbations, the administration of oral corticosteroids given for this indication will not fall under the definition of “chronic administration of immunosuppressants or other immune-modifying drugs at any time during the study period”, used to determine elimination from the ATP analysis of immunogenicity. • To add a benefit: risk assessment section (Section 1.3). 	
In addition, a typo in the footnote of the table of intervals between visits (Table 9) has been corrected and the list of contributing authors has been updated.	

Added text is presented in ***bold italics*** and deleted text in ~~strikethrough~~ in the following sections:

Title page

Contributing authors

- PPD (PPD) ***Novellas Healthcare*** for GSK Biologicals),
Study Delivery Manager

- PPD [REDACTED] and PPD [REDACTED], PPD [REDACTED] and PPD [REDACTED], Safety Representatives

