4. ENDPOINTS

4.1. Primary endpoints

- Occurrence of each solicited local adverse event (AE), during the 7-day follow-up period (*i.e.* day 0 - 6) following each vaccination, in all subjects.
- Occurrence of each solicited general AE, during the 7-day follow-up period (*i.e.* day 0 - 6) following each vaccination, in all subjects.
- Occurrence of any unsolicited AE, during the 30-day follow-up period (*i.e.* day 0 - 29) following each vaccination, in all subjects.
- Occurrence of each haematological/ biochemical laboratory abnormality at Day 0, Day 7, Day 30, Day 60, Day 67, Day 90, Day 270 and Day 450, in all subjects.
- Occurrence of any potential immune-mediated disease (pIMD) from first vaccination up to study conclusion, in all subjects.

Statistical Analysis Plan

Study alias & e-track number(s): NTHi-004 (200157)

- Occurrence of any serious adverse event (SAE) from first vaccination up to study conclusion, in all subjects.

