- The percentage of subjects having results below or above the local laboratory normal ranges will be tabulated by time point.
- The maximum grading from Screening up to study conclusion will be tabulated. Grades will be based on the FDA Guidance for Industry “Toxicity Grading Scale for Healthy Adults and Adolescent Volunteers Enrolled in Preventive Vaccine Clinical Trials” (see Appendix C of the protocol).

The number of subjects who experienced any **pIMD** or any **SAE** from from first vaccination up to 6 months post-Dose 2 will be reported will be reported.

The number of subjects who experienced any **AE leading to study withdrawal**, from first vaccination up to study conclusion, or any **SAE related to study participation of**

Statistical Analysis Plan

Study alias & e-track number(s): NTHi-004 (200157)

concurrent GSK medication/ vaccination, during the entire study period, will be reported.

Pregnancy reports from first vaccination up to 6 months after last vaccination and pregnancy outcomes will be described in detail.

The percentage of subjects/ dose using **concomitant medication/ product** (any medication/ product, any antipyretic and any antipyretic taken prophylactically, respectively) during the 7-day follow-up period (day 0 – day 6) and during the 30-day follow-up period (day 0 – day 29) will be summarised per group for each dose and overall per dose.

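### The only graded laboratory summary takes the maximum from Screening, so grades present before Dose 1 count as outcomes and dilute the group contrast

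*SAP*

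**What the plan says.** For each group and each haematology or biochemistry parameter, SAP Amendment 1 Section 6.1.1 plans two summaries:

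- an ungraded one: "The percentage of subjects having results below or above the local laboratory normal ranges will be tabulated by time point";
- a graded one, on the FDA scale in Protocol Appendix C: "The maximum grading from Screening up to study conclusion will be tabulated".

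Protocol 11.8 plans the same two. Neither text contains a maximum restricted to the period after Dose 1, a shift from baseline, or a rule for abnormalities that were already present.

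The corresponding primary endpoint is narrower: "Occurrence of each haematological/ biochemical laboratory abnormality at Day 0, Day 7, Day 30, Day 60, Day 67, Day 90, Day 270" and Day 450 (SAP 4.1). It lists scheduled days only, without Screening. It does include Day 0, which is sampled before Dose 1.

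On baseline status, Protocol 5.3 warns that in these COPD patients "various pre-existing haematological/biochemical abnormalities might be detected", and it excludes only abnormalities that the investigator judges clinically significant.

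At each AECOPD visit, "a volume of approximately 2 mL of whole blood will be collected for haematology parameters from all subjects" (Protocol 6.6.15.1), and "Haematology assays on whole blood taken at AECOPD visits will be performed in the same central laboratory" as the safety samples (Protocol 6.7.3). The Amendment 2 rationale in Protocol Appendix D gives the purpose: "This blood sample will be collected to describe the systemic inflammation at time of exacerbation".

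**The concern.** Describing safety is the primary objective, and laboratory abnormality is one of the primary endpoints. A worst grade over a period that opens 14-28 days before Dose 1 (Protocol Table 9) mixes two things: what subjects brought into the trial and what appeared after vaccination. The mixing is likely to matter here because pre-existing abnormalities are expected and the grading scale was written mainly for healthy volunteers.

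The rule also sits awkwardly with the protocol's own treatment of such findings. Under Protocol 9.1.4, an abnormality present at the start of the study that does not worsen is not reported as an adverse event. In the graded table it counts in full.

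A second uncertainty is the source of samples. The SAP applies the rule to each parameter without saying which draws supply the values. Blood counts taken during an exacerbation fall between Screening and study conclusion, so two programmers could build different tables from the same text.

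**Working it through.** **The plan's own figure.** The only quantitative statement about safety is in Protocol 11.4: with 70 subjects per group, more than 50% chance of seeing an event of 1% incidence and more than 97% at 5%. Both reproduce: 1 - 0.99^70 = 0.505 and 1 - 0.95^70 = 0.972. No figure is stated for laboratory grades, and group comparisons are declared descriptive (Protocol 11.13).

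**Inputs.** About 70 subjects per group, randomised 1:1 (Protocol 6.2.2.2). Everything else is assumed, because the documents give no laboratory rates:

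- b, the share already at or above a given grade before Dose 1, taken as similar in both groups because of randomisation;
- c and v, the risks of reaching that grade after Dose 1 among the remaining subjects, in Control and in 10-AS01E.

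**Formula.** The from-Screening table shows b + (1-b)c in Control and b + (1-b)v in the vaccine group. The difference is (1-b)(v-c), so the true new-onset difference is multiplied by (1-b).

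**Any grade, assumed c = 5% and v = 20%.**

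| b | Control | Vaccine | Difference (points) | Ratio |
|---|---|---|---|---|
| 0 (new onset only) | 5% | 20% | 15 | 4.0 |
| 10% | 14.5% | 28% | 13.5 | 1.93 |
| 20% | 24% | 36% | 12 | 1.50 |
| 30% | 33.5% | 44% | 10.5 | 1.31 |
| 50% | 52.5% | 60% | 7.5 | 1.14 |

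For example, at b = 20%: 0.20 + 0.80 x 0.05 = 0.24 and 0.20 + 0.80 x 0.20 = 0.36. With 70 per group, 15 points is 10.5 subjects and 7.5 points is 5.25 subjects.

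With other assumed risks (c = 10%, v = 30%) the pattern is the same. The difference falls from 20 points to 18-10, and the ratio from 3.0 to 1.95-1.18, for b of 10-50%.

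**Grade 3 or higher, assumed c = 1%, v = 8%, b = 5%.** Control 0.05 + 0.95 x 0.01 = 5.95%; vaccine 0.05 + 0.95 x 0.08 = 12.6%. The difference is 6.65 points against 7.0, so 6.65/7.0 = 95% of it remains. The ratio falls from 8.0 to 2.1.

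**If AECOPD counts were also included.** Suppose they grade a further independent share e in each group. The shares become 1 - (1-b)(1-c)(1-e) and 1 - (1-b)(1-v)(1-e). With b = 20%, c = 5% and v = 20%:

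- e = 10%: 31.6% v 42.4%, difference 10.8 points, ratio 1.34;
- e = 30%: 46.8% v 55.2%, difference 8.4 points, ratio 1.18.

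This step applies only if the wording is read to include those samples.

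**The case against.** The strongest reply is that the endpoint is defined by time point, and the first of the two tables reports it that way, by group. Day 7, 30, 67 and 90 can be read against Day 0 and against randomised placebo. That stands as real mitigation. The table is ungraded, however, and it shows percentages of the group. It cannot say whether the same subjects were abnormal before vaccination or whether anyone's grade rose.

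Three stronger readings are tempting, and the documents do not support them.

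- *The table hides any vaccine effect, because a subject graded at Screening stays in that category.* A maximum still moves up: Grade 1 at Screening and Grade 3 at Day 7 is tabulated as Grade 3. Only a later abnormality of equal or lower grade is lost. For haemoglobin, the Appendix C scale also has rows graded on change from baseline.
- *The table is systematically tilted towards one group.* Pre-vaccination grades should be similar between randomised groups in expectation, so their effect is attenuation and noise.
- *Exacerbation blood counts will be pooled into the safety table.* Protocol Table 10 lists them as a separate sample type, their stated purpose is not vaccine safety, and the endpoint names scheduled days only. The more natural reading excludes them. What remains is that the SAP does not say so.

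Other safeguards exist. Clinically significant abnormalities that worsen from baseline are reported as adverse events, within the reporting windows (Protocol 9.1.4). Holding rule 2c looks at Grade 3 or higher at day 7 after vaccination. Individual listings are produced at the final analysis. Table layouts are in a separate annex that is not among the documents reviewed, so a shift display there cannot be ruled out; the point concerns the protocol and SAP text.

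**Conclusion.** The point holds as a dilution of the graded laboratory comparison. As written, the rule counts pre-vaccination grades as outcomes and multiplies the absolute group difference by (1-b). For any-grade abnormalities under the assumed 20% v 5%, that means 13.5-7.5 points in place of 15 and a ratio of 1.93-1.14 in place of 4.0, for b between 10% and 50%. For Grade 3 or higher the absolute loss is small when baseline prevalence is low, about 5% of the difference at b of 5%.

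These sizes rest on assumed b, c and v. The factor (1-b) itself needs only a similar baseline share in the two groups. No test or trial decision hangs on this table, and the by-time-point summary offsets part of the loss. The point is still worth correcting, because the table is the only graded view of a primary safety endpoint in the text and a better one needs no new data. The AECOPD samples are a matter of missing wording, not a stated plan to include them.

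**What to change.** In SAP Section 6.1.1, replace the graded summary by the following, for each group and parameter:

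- the maximum grade over scheduled safety samples after Dose 1: Day 7, 30, 60, 67, 90, 270 and 450 in the final analysis, and Day 7 to Day 90 in the first-step analysis;
- cross-tabulated by the last grade before Dose 1 (Day 0, or Screening if Day 0 is missing);
- with the number of subjects whose grade increased from that baseline.

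The cross-tabulation is essential. Moving the start of the window alone would still count a chronic abnormality that persists after Dose 1.

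Add one sentence stating that haematology drawn at AECOPD visits is excluded from this table and reported separately. Align Protocol 11.8, or record the change in SAP Section 9.

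The cost is SAP wording and one additional shift table per parameter. Screening, Day 0 and all later safety samples are already scheduled for every enrolled subject.

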6.1.2. Analysis of immunogenicity

The analysis will be performed on the ATP cohort for immunogenicity. If the percentage of vaccinated subjects with serological results excluded from the ATP cohort for analysis of immunogenicity is more than 10%, a second analysis will be performed on the TVC.

Humoral immune response

Within group evaluation

For each group, at each time point during which blood samples are collected for humoral immune response and for each assay:

- Seropositivity rate and their exact 95% CI will be tabulated.
- GMCs and their 95% CI will be calculated.

For each group, at each time point during which blood samples are collected for humoral immune response:

- Antibody concentrations distribution will be investigated using Reverse Cumulative Curves.

Between groups evaluation

Comparative analyses will be exploratory with the aim to characterise the difference between the 2 groups in humoral immune response.

The difference in terms of GMCs will be evaluated at 1 month post-Dose 2 and at Day 450 by computing the 95% CIs of the GMC ratio between groups by using an ANCOVA model that considers heterogeneity of variances (via Proc Mixed) on the logarithm10 transformation of the concentrations. This model will include the country, the group, age category (40 - 59 years or 60 - 80 years), number of moderate and severe AECOPD in the year before vaccine Dose 1 (< 2 or \geq 2), GOLD grade (GOLD 2 or GOLD 3) and pre-Dose 1 concentration (as covariate) as fixed effects.

Statistical Analysis Plan

Study alias & e-track number(s): NTHi-004 (200157)

However, these differences should be interpreted with caution considering that there will be no adjustment for multiplicity of endpoints.

Cell-mediated immune response

The frequency of specific CD4⁺/ CD8⁺ T-cells will be summarised (mean, SD, minimum, Q1, median, Q3, and maximum) by group, at each time point during which blood samples are collected for CMI (descriptive statistics).

Each data will be obtained by subtracting the summary of the background value to each summary value. Values less than or equal to zero will be set to 1 for the purpose of geometric mean calculation and graphical representation.

6.1.3. Analysis of impact of the investigational vaccine on AECOPD incidence

The analysis will be performed on the ATP cohort for efficacy. If the percentage of vaccinated subjects excluded from the ATP cohort for efficacy is more than 10%, a second analysis based on the TVC will be performed to complement the first analysis.

The following incidence rates will be computed over a period starting 1 month post-Dose 2 and lasting for 1 year, with 95%CI:

- NTHi-associated moderate and severe AECOPD. (See definition in section 7.1.4)
- NTHi-associated all-severity AECOPD.
- All-cause moderate and severe AECOPD.
- All-cause, all-severity AECOPD.

Vaccine efficacy (VE) for AECOPD events will be defined as:

$$VE (AECOPD) = 1 - R_{vaccine} / R_{control}$$

with:

- $R_{vaccine}$ = average yearly incidence rate of AECOPD events per subject in the group 10-AS01E.
- $R_{control}$ = average yearly incidence rate of AECOPD events per subject in the Control group.

In case the 95% CI of the VE cannot be estimated, *e.g.* when no event is observed in the group 10-AS01E (leading to a VE of 100%), then an exact procedure will be used to estimate a VE and its 95% CI. This exact procedure will be based on the number of subjects with event instead of on the average number of event per subject in each group.

Statistical Analysis Plan

Study alias & e-track number(s): NTHi-004 (200157)

VE in the prevention of NTHi-associated moderate and severe AECOPD and its 95% CI will be calculated.

VE in the prevention of NTHi-associated all-severity AECOPD, of all-cause moderate and severe AECOPD and of all-cause, all-severity AECOPD and their 95% CI will also be calculated.

The 95%CI of the incidence rate will be computed using a model which accounts for repeated events. The Generalised linear model assuming the Negative Binomial distribution for the response variable with logarithm as link function, and the logarithm of time for follow-up as an offset variable will be used. In addition, the following covariates (as per randomization) will be taken into account:

- country,
- number of moderate/severe exacerbations reported in the 12 months prior to enrolment,
- COPD status at enrolment (derived by GSK from the Visit 1 spirometry results)
- Age (below or equal to median/above median)

If the model does not converge, the Poisson distribution will be used instead of the Negative Binomial one.

The frequency of all these AECOPDs will be presented. The estimated incidence rate with 95%CI of AECOPDs in which Hi (resp. Mcat, Sp) is present in culture and was not present in the previous visit estimated by a Generalised linear model assuming the Negative Binomial distribution will be estimated.

Time to first AECOPD event by baseline status - Cox regression model

The Cox's regression model including the risk factors:

- country,
- number of moderate/severe exacerbations reported in the 12 months prior to enrolment,
- COPD status at enrolment (derived by GSK from the Visit 1 spirometry results)
- Age (below or equal to median/above median)

as covariates (as per randomization) will be performed to model the time until the first occurrence of AECOPD episodes. Additional stratification/risk factor may be defined during the analyses like sex factor as exploratory analysis.

Statistical Analysis Plan

Study alias & e-track number(s): NTHi-004 (200157)

